The proposed research will empirically test our hypotheses by accomplishing **two specific aims**: (1) determine if EAA elevates basal rates of muscle protein synthesis by up-regulating anabolic pathways and cyto-protective proteins, and inactivating catabolic pathways in the short term vs. Placebo and (2) determine if short-term prevention of atrophy, weakness, and functional mobility leads to positive changes in muscle cell structure and function, and improved quality of life in the longer term vs. Placebo. The proposed work is significant because it advances knowledge of the molecular and cellular changes occurring during muscle atrophy (Placebo) and atrophy prevention (EAA) in a clinical setting using a treatment that is broadly applicable, is well tolerated, and can be implemented immediately.

INTRODUCTION AND BACKGROUND

In the coming decades, the demand for primary total knee arthroplasty (TKA) in the U.S. is projected to increase 673% to 3.4 million surgeries performed annually. TKA surgery is primarily performed on older adults and results in significant muscle atrophy in the operative and non-operative thigh (quadriceps and hamstrings), which compromises balance, impairs functional mobility, and dramatically increases the risk of falls and related injuries. For older adults, muscle atrophy occurring during periods of inactivity or following surgery may be more difficult to recover.

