Quadriceps weakness results from both muscle atrophy and neural activation deficits (80, 107). In the longer term however, strength deficits are due to persistent muscle atrophy, explaining 77% of the quadriceps strength deficits 1 year post-TKA (80). Our preliminary data show that EAA supplementation reduces strength loss and accelerates the return of functional mobility. Persistent quadriceps atrophy and weakness have profound effects on functional mobility and activities of daily living (13, 107, 119). It

is well known that quadriceps mass and strength are strong predictors of functional mobility (i.e., timed up-and-go, stair-climb down [descent] ability and ambulation).

We also have compelling preliminary data showing that Type II muscle cell cross-sectional area (CSA) is reduced (atrophied) compared to controls following TKA. We expect to show that CSA increase (normalize to that of the non-operative side) in the EAA group. As well, we have preliminary data from isolated muscle fiber bundle analysis of oxygen consumption (mitochondria respiration) from muscle cells from TKA subjects have lower (-61%) basal mitochondrial function (respiration) vs. age- and sex-matched controls.

Contribution to Scientific Knowledge.

Muscle atrophy occurs in cancer cachexia (12), chronic heart failure (8), chronic obstructive pulmonary disease (70), HIV-AIDS (121, 124), renal failure (66), rheumatoid arthritis (71, 77), osteoarthritis (116), burn injury (18), following total hip and knee arthroplasty (58), ACL reconstruction (57), and during bed rest (94). Despite its widespread impact in clinical settings little progress has been made in devising ways to prevent muscle atrophy. As such, our R01 proposal is significant because it has broad clinical appeal as a high yield therapy to attenuate atrophy under a variety of clinical conditions (EAA are well tolerated, easily digested, and immediately available).

The significance of this Research Plan also centers on our use of TKA as a model system for the study of muscle atrophy (Placebo) and atrophy prevention (EAA), which are due to an imbalance between anabolic and catabolic alterations at the molecular and cellular level. *Our study will advance knowledge of the molecular and functional changes that are occurring during muscle atrophy and prevention in older males and females, and will identify additional novel targets for therapeutic interventions.*

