Our study is innovative for several reasons. Foremost is our translational approach which will allow us to identify novel molecular regulators of muscle atrophy (Placebo) and atrophy prevention (EAA). Using isotopically labeled tracer methodologies we will quantify muscle protein synthesis and breakdown, and link those results with changes in muscle volume, strength and functional mobility. We will also determine the degree to which short-term preservation of muscle volume, strength and function translate into longer-term structural and functional (mitochondrial respiratory) adaptations at the cellular level. Our plan to explore potential sex differences in the age-related changes in muscle protein synthesis and breakdown following TKA and the mechanistic effects of EAA on muscle metabolism, atrophy, and mobility is exciting. Finally, this research plan brings together a clinical and translational research team to investigate the biochemistry and physiology of muscle atrophy and incorporates functional measures of mobility and quality of life in a unique and meaningful way.

The primary innovation is our integration of cellular and molecular methods with measures of muscle protein synthesis and breakdown, volume, and functional mobility in order to better understand how muscle atrophy can be prevented in a clinical setting(s). Our protocol will be freely available to clinicians, therapists, and researchers interested in mitigating muscle atrophy, which may profoundly affect the medical/rehabilitation field as the use of EAA in atrophy prevention spreads and gains momentum.

Hypothesis.

The working hypothesis, based on strong preliminary results, is that twice-daily ingestion of 20 g of EAA for 1 week before and 6 weeks after TKA, will increase basal rates of muscle protein synthesis via inactivation of catabolic signaling (FoxO3a), and up-regulation of anabolic (SLC36A2, IGF-I & VEGF) and cyto-protective proteins (ATF4 & REDD1). We further propose that short-term atrophy prevention and accelerated return of functional mobility will translate into long-term (6 months post-TKA) structural (cross-sectional area, CSA) and functional (mitochondrial respiration) adaptations, leading to improved quality of life in TKA patients vs. Placebo in older men and women.

SPECIFIC AIMS

To test our hypothesis our *Research Plan* proposes scientifically rigorous methods designed to achieve the following specific aims:

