- 1.6 *Does EAA influence markers of mitochondria function vs. Placebo?*
- 1.7 *Does statin use influence cell respiration over time?*
- 1.8 *Does EAA affect primary cell derived myocyte function over time?*
- **Specific Aim #2 (Physiology): Determine if short-term prevention of atrophy, weakness, and functional mobility leads to positive changes in muscle cell structure and function, and quality of life in the long term (6 months post-TKA) vs. Placebo.**
Successful completion of Aim 2 will identify a role for EAA supplementation in clinical settings using a mechanistic approach. Our approach is based on strong preliminary clinical data from older men and women following TKA demonstrating that EAA supplementation for 1 week prior to, and for 2 week post-TKA was effective in preventing significant muscle atrophy (37). However, our preliminary data suggest that in the EAA group, atrophy at 2 weeks post-TKA was half that at 6 weeks in the operative quadriceps and hamstrings. This potential 'catch-up' muscle loss was not observed in the non-operative leg within the EAA group but was identical to the change from 2 weeks to 6 weeks in the operative leg of the Placebo group. We interpret these data to support the need to supplement for 6 weeks post-TKA in order to maximally prevent bilateral muscle atrophy.

The proposed research design will answer the following questions:

- 2.1 *Does EAA prevent short-term (7 wk post-TKA) bilateral muscle atrophy, preserve quadriceps strength, and accelerate the return of functional mobility vs. Placebo?*
- 2.2 *Are there short-term sex differences on the above outcome measures?*
- 2.3 *Will EAA increase long-term (6 mo post-TKA) quadriceps functional mobility vs. Placebo?*
- 2.4 *Does EAA improve longer-term (6 mo post-TKA) functional mobility and measures of quality of life vs. Placebo?*
- 2.5 *Are there long-term sex differences in functional mobility or measures of quality of life?*
- 2.6 *Does inhibition of angiogenic factors (IFG-1 & VEGF) inhibit a pro-angiogenic response?*
- 2.7 *Does EAA influence markers of inflammation vs. Placebo?*
- 2.8 *Does EAA influence markers of mitochondrial function vs. Placebo?*
- 2.9 *Does statin use influence cell respiration over time?*
- 2.10 *Does EAA affect primary cell derived myocyte function over time?*

Methods, Materials and Analysis

Study Design.

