**Inpatient Research Protocol & Integration w/ Standard Patient Care: Protocol while subject is inpatient (IP) on orthopedic floor (estimate 2 to 3 days as IP); Daily AM fasting blood draw by phlebotomist on POD 0 and POD 2. (leave blood on ice, research staff to pick up); Subject to don accelerometer at all times; Twice daily ingestion of supplement (subject and investigators are blinded to treatment group); Ingestion will occur 1 hour after daily physical therapy; Inpatient physical therapy to begin at 9 AM and 1 PM. Therapy per MD/PT standard Tx; Twice daily ingestion of deuterium oxide (D₂O); Daily food-log recordings (all nutrient intake) by subject. Research staff and nursing to remind subject to complete this task.

Specific Aim #2 (Physiology).

Aim #2 - Determine if short-term prevention of atrophy, weakness, and functional mobility leads to positive changes in muscle cell structure and function, and quality of life in the long term (6 months post-TKA) vs. Placebo.

Randomization Assignments.

- Aim #2, Trial #1 enrolled 19 patients before closing enrollment in June 2018. Please refer to the Event Form submitted on June 4, 2018 for additional details. Please refer to study protocol December 2017 for information on Aim #2, Trial #1 EAA proportions and protocols.
- Aim #2, Trial #2 (reflected throughout the protocol as "Aim 2") will consist of 2 groups (N=40/group through protocol completion; EAA vs. Placebo) that are identical in protocol design. Up to 160 patients will be consented to achieve 40 per group completion.

Summary of Study-Related Activities.

- Patient questionnaires before and after surgery
- Functional mobility tests before and after surgery
- Accelerometer before surgery and after surgery
- Optional muscle biopsy before and after surgery

Changes to Study-Related Activities.

Omitted Procedures or Measures for Participants Enrolled in Aim #2

- No strength & central activation testing
- No consumption of heavy water (D₂O)
- No muscle biopsies at surgery, 1 week or 2 weeks post-TKA operation
- No blood draws
- No MRIs performed
- No Three day food diary
- Removal of 6 minute walk
- Removal of study questionnaires at 2 weeks post-TKA (functional testing remains)

New or Altered Study Procedures or Measures for Participants Enrolled in Aim #2.

- New study assessment time points: 3 months & 6 months
- Optional (patient choice at enrollment) muscle biopsies at pre-op, 6 weeks & 6 months post-TKA

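### Aim 2 Trial 2 collects no quadriceps strength or whole-muscle volume, yet still poses those questions; its mean effect size is mislabelled and its detectable effects fit 30, not 40, per group

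*Combined protocol and SAP*

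**What the plan says.** Under Specific Aims, the protocol says the Aim 2 design will answer question 2.1: "Does EAA prevent short-term (7 wk post-TKA) bilateral muscle atrophy, preserve quadriceps strength, and accelerate the return of functional mobility vs. Placebo". Question 2.2 asks about sex differences on the same measures. The aim itself, in the Project Summary and again under Specific Aim #2, is to "determine if short-term prevention of atrophy, weakness, and functional mobility leads to positive changes in muscle cell structure and function". Contribution to Scientific Knowledge promises to determine how far "short-term preservation of muscle volume, strength and function translate into longer-term structural and functional (mitochondrial respiratory) adaptations".

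The Specific Aim #2 section describes a different study. It says that "Aim #2, Trial #1 enrolled 19 patients before closing enrollment in June 2018" and that Aim 2 elsewhere in the protocol means Trial 2, with 40 completers per group. Its list of omitted procedures includes "No strength & central activation testing", "No MRIs performed" and "Removal of 6 minute walk". The Aim 2 primary outcomes are the Aim 1 secondary outcomes less these omissions. Biopsies are at the patient's choice, before surgery and at 6 weeks and 6 months.

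Data Analysis still names bilateral atrophy and quadriceps strength among the hypotheses the sample size serves, and still plans to model muscle and strength over time. For Aim 2 it gives an average preliminary effect of d = 1.01, said to span every Aim 2 outcome. For 40 completed subjects per group at 85% power, it gives detectable effects of .79 with no covariate, .68 with a pretest correlation of .50, and .52 with .75.

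**The concern.** A question that the plan says will be answered needs a measurement behind it. Trial 2 has none for quadriceps strength or whole-muscle volume. Grip strength and the chair stand remain, but neither is a test of quadriceps strength. Only Aim 2 follows patients beyond 6 weeks, so the promised link from early muscle volume and strength to later cell changes has no data from current enrolment.

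The power paragraph has two further faults. It presents an average made up mostly of uncollected measures as evidence about the Aim 2 outcomes, and its detectable effects do not fit the stated sample size. A reader of the eventual report could take mobility or fibre results as evidence on strength or muscle mass. A reader could also quote design sensitivity figures that belong to a different trial size.

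**Working it through.** **1. Question against measurement (Trial 2).**

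| Element of question 2.1 or the aim | Trial 2 measurement |
|---|---|
| Quadriceps strength, weakness | None; strength and central activation testing omitted |
| Whole-muscle atrophy | None; MRI omitted |
| Fibre-level atrophy | CSA from optional biopsies |
| Functional mobility | Timed up-and-go, stairs, chair stand, balance, 4-metre walk, grip; all participants, to 6 months |

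Reading atrophy at fibre level is legitimate. Preliminary Studies (Physiology) reports that "Type II muscle cell cross-sectional area (CSA) is reduced (atrophied) compared to controls following TKA". Two limits apply.

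- *Who is biopsied.* The Muscle biopsy risk section gives biopsies for N=80 (40/group) in Aim 2, directly after saying that Aim 2 patients may decline them. Patients enrolled less than 4 weeks before surgery are not eligible for biopsy, and the biopsy criteria exclude those on oral blood thinners. With 40 completers per group in total, any opt-out or ineligibility among them puts the number below 40.
- *How CSA is expressed.* Under Primary Biochemical Outcome Measures, CSA is percent change from baseline, made relative to the non-operative leg. That metric alone cannot show preservation in the non-operative leg, which the word bilateral requires.

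**2. The d = 1.01 average.** The inputs are the eight physiological and functional effects under Effect sizes, all percent change from baseline to 6 weeks.

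- All eight: (1.52 + .90 + 1.05 + .66 + 1.03 + 1.08 + 1.13 + .70)/8 = 8.07/8 = 1.009. The plan's figure reproduces.
- Five dropped (two volume, two strength, six-minute walk): (1.52 + .90 + 1.05 + .66 + .70)/5 = 4.83/5 = 0.97.
- Three retained (timed up-and-go, stair ascent, stair descent): (1.03 + 1.08 + 1.13)/3 = 3.24/3 = 1.08.

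The arithmetic is right and the label is wrong. No effect is listed for 6 months, questionnaires, other functional tests, or the Aim 2 biopsy outcomes (CSA, respiration).

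**3. Detectable effects.** The inputs from Data Analysis are two-tailed α = .05, 85% power and 1:1 allocation. I solved for d in

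power = P(T′ > t(.975, df)), where T′ is noncentral t with noncentrality d·√(n/2)/√(1 − r²), and df = 2n − 2 (one fewer with the covariate).

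| n per group | no covariate | r = .50 | r = .75 |
|---|---|---|---|
| **Aim 2 as stated (40)** | **.79** | **.68** | **.52** |
| 40 | .678 | .588 | .449 |
| 30 | .787 | .682 | .521 |
| **Aim 1 as stated (20; 10 for metabolic studies)** | **1.10** | **.95** | **.72** |
| 20 | .972 | .843 | .644 |
| 16 | 1.095 | .949 | .725 |
| 10 | 1.417 | 1.232 | .941 |

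Normal-approximation check at 40 per group: (1.960 + 1.036)·√(2/40) = .670. The stated Aim 2 set is consistent within itself (.79·√(1 − .25) = .684; .79·√(1 − .5625) = .523), so the same n lies behind all three values. That n is 30. At 40 per group, the power for .79, .68 and .52 in their respective covariate settings is 93.7%, 93.4% and 93.5%, not 85%.

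**4. Retained mobility tests.** Taking each preliminary d at face value in a two-sample comparison with 40 per group, power is 99.5% (timed up-and-go), 99.8% (stair ascent) and 99.9% (stair descent).

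**5. Fibre CSA.** If 10, 20, 30 or 40 per group have biopsies, the detectable d without a covariate is 1.42, .97, .79 or .68. Only 40 is printed in the protocol; the smaller numbers are assumptions.

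**The case against.** The Specific Aim #2 section makes the current procedures plain, so much of this is unrevised grant text that will mislead few readers. The error in the detectable effects favours caution. Both points are fair. They limit the consequence, but they do not make the text correct.

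An unstated attrition allowance could explain the figures, since 30/40 = 75% and 16/20 = 80%. The power paragraph, however, speaks of completed subjects, and up to 160 patients are to be consented to reach 40 completers per group. The documents therefore give no basis for a second allowance.

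The Aim 2 analysis covers Trials 1 and 2, and Trial 1 ran under a December 2017 protocol that is not among these documents. If Trial 1 measured strength or volume, deleting those terms outright would discard a question for collected data. That stands, and it is why the remedy is a scope label rather than deletion.

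The power figures in step 4 also need care. The plan says its effect sizes were computed after adjustment for pretest and covariates, so it is doubtful to call this no-covariate power. The effects are preliminary, and Aim 2 has since changed the supplement composition and lowered the age floor to 40. The figures show only that dropping measures did not weaken the retained tests on the plan's own assumptions.

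Appendix 1, which tags MRI and isometric strength for Aim 1 only, is weak support. It tags the accelerometer the same way, although the Aim 2 schedule includes it.

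**Conclusion.** The plan is wrong as written on three points.

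- Trial 2 cannot answer the strength part of question 2.1, any whole-muscle reading of bilateral atrophy, or the matching parts of 2.2. It cannot inform quadriceps weakness in the aim.
- The d = 1.01 is not an average over the Aim 2 outcomes; five of its eight components are not collected.
- The Aim 2 detectable effects should read .68/.59/.45 for 40 completers per group. Aim 1's 1.10/.95/.72 fits about 16 per group, and neither 20 nor 10.

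Three stronger readings are tempting and are not supported. First, a reader might infer that Aim 2 is underpowered. The retained effects average 1.08, above 1.01, and 40 per group detects smaller effects than stated. Second, a reader might infer that atrophy is untestable in Trial 2. Fibre CSA can address it, in a voluntary subset whose stated size is inconsistent and probably below 40 per group. Third, a reader might infer that no Aim 2 participant had strength or volume measured. The documents do not say what Trial 1 collected.

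The conclusion assumes a standard two-group comparison with variance reduced by 1 − r². This should be fixed, but it does not threaten the mobility comparisons.

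**What to change.** 1. In questions 2.1 and 2.2, the Aim 2 title, Contribution to Scientific Knowledge, Power analyses and Random coefficients analysis, state that quadriceps strength or weakness and whole-muscle volume are not assessed in Aim 2 Trial 2. Keep them for Trial 1 only if its protocol collected them. State that atrophy in Trial 2 means fibre CSA in the voluntary biopsy subset, reported for each leg separately if the word bilateral stays.
2. Under Power calculations, replace the d = 1.01 sentence with the three retained 6-week effects (timed up-and-go 1.03, stair ascent 1.08, stair descent 1.13). Say that no planning effect is given for 6 months, questionnaires, other functional tests or biopsy outcomes.
3. Restate the Aim 2 detectable effects as .68/.59/.45 for 40 completers per group, or state that .79/.68/.52 assume 30 analysable per group. Correct or explain the Aim 1 figures in the same way.
4. Reconcile the biopsy count of N=80 in the Muscle biopsy risk section with the optional-biopsy text there and under Specific Aim #2. Reconcile the Aim 2 strength-testing entry in Table 3 (clear in the orthopedic clinic row, ambiguous in the laboratory row) with the omitted-procedures list. Do the same for the six-minute walk in the Aim 2 website text and Appendix 1.

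The causal verb in the Aim 2 title is a separate matter and need not change here; softening it would blur the randomised contrast with placebo. No procedure is added and no collected outcome is removed. The cost is wording changes and a narrower stated claim for Aim 2.
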